### **Hepatitis**

13. A locally performed hepatitis B (HBV) test is required during screening. Patients who are HBV surface antigen positive are eligible if they have received HBV anti-viral therapy for at least 4 weeks and have undetectable HBV viral load before study entry (ICF signature). Patients should remain on anti-viral therapy throughout study treatment and follow local guidelines for HBV anti-viral therapy post completion of study interventions.
14. A locally performed hepatitis C (HCV) test is required during screening. Patients with history of HCV infection are eligible if HCV viral load is undetectable at screening. Patients must have completed anti-viral therapy at least 4 weeks before study entry (ICF signature).

---

## Special requirements for female patients and contraception

15. A female patient is eligible to participate if she is not pregnant, not breastfeeding, and one of the following conditions applies:
  - 15.1. Not a woman of childbearing potential (WOCBP). A WOCBP is defined as fertile, following menarche and until becoming post-menopausal unless permanently sterile. Permanent sterilization methods include hysterectomy, bilateral salpingectomy, and bilateral oophorectomy. A postmenopausal state is defined as no menses for 12 months without an alternative medical cause. A high follicle stimulating hormone level in the postmenopausal range may be used to confirm a post-menopausal state in women not using hormonal contraception or hormonal replacement therapy. However, in the absence of 12 months of amenorrhea, a single follicle stimulating hormone measurement is insufficient.
  - 15.2. A WOCBP who agrees to use a highly effective contraceptive method during the treatment period and for at least 120 days after the last dose of pembrolizumab or at least 30 days after the last dose of nanrilefusp alfa, whichever is later
    - WOCBP can only be included after a negative serum pregnancy test at screening.
    - Highly effective contraception includes:
      - Combined (estrogen- and progestogen-containing) hormonal contraception associated with inhibition of ovulation:
        - Oral
        - Intravaginal
        - Transdermal
      - Progestogen-only hormonal contraception associated with inhibition of ovulation:
        - Oral
        - Injectable
        - Implantable
      - Intrauterine device
      - Intrauterine hormone-releasing system
      - Bilateral tubal occlusion
      - Vasectomized partner provided the partner is the sole sexual partner of the WOCBP trial participant and that the vasectomized partner has received medical assessment of the surgical success
      - Sexual abstinence defined as refraining from heterosexual intercourse during the entire treatment period and for at least 120 days after the last dose of pembrolizumab or at least 30 days after the last dose of nanrilefusp alfa, whichever is later. The reliability of sexual abstinence needs to be evaluated in relation to the duration of the clinical trial and the preferred and usual lifestyle of the patient.
16. Male patients must agree to use a condom during the treatment period and for at least 120 days after the last dose of pembrolizumab or at least 30 days after the last dose of nanrilefusp alfa, whichever is later.

## 5.2 Exclusion criteria

Patients will be excluded from the study if any of the following criteria apply:

### Prior/concomitant therapy

1. Has received prior therapy with an anti-PD-1, anti-PD-L1, or anti-PD-L2 agent or with an agent directed to another stimulatory or co-inhibitory T-cell receptor (e.g., cytotoxic T-lymphocyte antigen 4, CD134 [OX40], CD137), and was discontinued from that treatment due to a grade  $\geq 3$  AE
2. Prior exposure to drugs that are agonists of IL-2 or IL-15
3. Prior systemic anti-cancer therapies, including investigational agents, before the first dose of study medication (day 1 of cycle 1):
  - 3.1. Less than 4 weeks for systemic chemotherapy and immuno-oncology therapies; and for tyrosine kinase inhibitors 4 weeks or 5 half-lives (whichever is shorter)
  - 3.2. Less than 4 weeks from major surgeries and not recovered adequately from the procedure and/or any complications from the surgery
4. Has received prior radiotherapy within 2 weeks of the start of study interventions or have had a history of radiation pneumonitis.

Note: Patients must have recovered from all radiation-related toxicities and not require corticosteroids. A 1-week washout is permitted for palliative radiation ( $\leq 2$  weeks of radiotherapy) to non-central nervous system disease.

5. NSCLC indication only: Has received radiation therapy to the lung that is  $>30$  Gy within 6 months of the first dose of study interventions
6. Has received a live or live-attenuated vaccine within 30 days prior to the first dose of study interventions

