#### Disease characteristics

4. Patients with the following histologically or cytologically confirmed solid tumor indications and line of treatment:
  - NSCLC
    - For the second-line or third-line treatment of patients with advanced and/or metastatic NSCLC with disease progression on or after an immune checkpoint inhibitor-containing regimen and a platinum-containing regimen, with no EGFR or ALK genomic tumor aberrations, and who are not amenable to curative treatment
  - Colorectal cancer
    - For the first-line treatment of patients with unresectable or metastatic MSI-H/dMMR colorectal cancer
  - cSCC
    - For the first-line treatment of patients with recurrent or metastatic cSCC or second line if refractory or relapsed after an immune checkpoint inhibitor-containing regimen, and in whom radiotherapy is not feasible (based on data from study SC103 [AURELIO-03])
  - Advanced hepatocellular carcinoma (not applicable in France)
    - For the second- to fourth-line treatment of patients with advanced hepatocellular carcinoma having progressed on or after a checkpoint inhibitor-containing regimen
  - mCRPC
    - For the second- to fifth-line treatment of patients with mCRPC after recurrence or failure of docetaxel and prior treatment with abiraterone, enzalutamide, or any other androgen receptor-targeted agent
  - Ovarian cancer
    - For the second- to fifth-line treatment of patients with advanced ovarian cancer after recurrence or failure on the last platinum-based therapy within 6 months
5. Have measurable disease per RECIST 1.1 as assessed by the local site investigator/radiology; lesions situated in a previously irradiated area are considered measurable if progression has been demonstrated in such lesions

mCRPC: Patients with both measurable and non-measurable disease will be enrolled. At least 35 patients with measurable disease will be enrolled. Patients with no measurable disease and only widespread bone disease must have a CTC count of  $\geq 5$  cells per 7.5 mL of blood.

6. Availability of tumor tissue from a fresh biopsy at screening unless the biopsy cannot be obtained due to safety reasons or non-accessibility of the tumor site. If it is not possible to obtain a fresh biopsy, every effort should be taken to retrieve an archival biopsy. Archived, fixed tumor tissue may only be collected if taken preferentially after completion of the most recent systemic tumor therapy and within 12 months prior to the first dose of study treatment.

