#### **8.1.1.1 Initial tumor scans**

Initial tumor scans at screening must be performed within 28 days prior to day 1 of cycle 1. The site study team must review screening scans to confirm the patient has measurable disease per RECIST 1.1.

Tumor scans performed as part of routine clinical management are acceptable for screening if they are of acceptable diagnostic quality and performed within 28 days of day 1 of cycle 1.

If brain scans are performed to document the stability of existing metastases, the brain MRI should be acquired during screening. If MRI is medically contraindicated, CT with contrast is an acceptable alternative.

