### 9.3 Statistical analyses

#### 9.3.1 General considerations

Analyses will be descriptive (i.e., without a comparison). Efficacy analyses will be performed for each indication separately. Safety will be analyzed as described in section [9.3.3](#).

Summary statistics will include:

- Counts and percentages (categorical data)
- Number of observations, mean, standard deviation, median, minimum, and maximum (continuous data)

The ORR, iORR, BOR, iBOR, CBR, iCBR, CTC response, and PSA response will use the exact method based on the binomial distribution[56](#) to derive 95% confidence intervals (CIs).

---

Kaplan-Meier estimations and estimations of median (if reached) with log-log 95% CI, Q1 (25th percentile), and Q3 (75th percentile) will be used for time to confirmed PSA progression (mCRPC only), DoR, iDoR, PFS, iPFS, TtR, iTtR, and OS. In case of a confirmed response or disease progression, the date of the first tumor assessment or PSA evaluated as response or progression will be used for the time-to-event variables.

Depending on the amount of missing data, a sensitivity analysis will be performed for time-to-event endpoints. If such an analysis is planned, it will be described in the final Statistical Analysis Plan (SAP).

The last value of PSA, CTC count, CT scan, bone scan, or MRI on or up to 28 days before the date of the first study treatment will be used as the baseline value for each assessment. Only tumor assessments prior to or at the date of initiation of further-line therapy and using CT scan, bone scan, or MRI will be used for the evaluation of tumor response.

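### A lesion can be irradiated after its baseline scan and still serve as a target lesion, so shrinkage from radiation can count toward the single-arm ORR

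*Protocol*

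**What the plan says.** **Age of the baseline scan.** Protocol 8.1.1.1: "Initial tumor scans at screening must be performed within 28 days prior to day 1 of cycle 1". The same section and the footnotes to the Schedule of activities (1.3.1) accept routine-care scans of adequate quality from that window. Protocol 9.3.1 makes the last scan "on or up to 28 days before the date of the first study treatment will be used as the baseline value for each assessment".

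**Radiotherapy before the first dose.** Protocol 5.2, criterion 4 excludes a patient who "Has received prior radiotherapy within 2 weeks of the start of study interventions". Its note shortens this for short palliative courses outside the central nervous system: "A 1-week washout is permitted for palliative radiation".

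**Irradiated lesions.** Protocol 5.1, criterion 5: "lesions situated in a previously irradiated area are considered measurable if progression has been demonstrated in such lesions". It does not say whether the progression must come after the irradiation, or whether the status of the lesion is judged at the scan or at the first dose.

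**Radiotherapy on study.** Protocol 6.8.2 prohibits radiotherapy during the study. It allows palliative treatment of lesions that are not indicator lesions, and leaves a symptomatic solitary lesion or the brain to the investigator's discretion.

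**Scoring.** SAP 10.13.5 measures tumor burden as percent change from the baseline sum of target lesions. SAP 10.13.3 derives best overall response from the first dose until progression, death or new anti-cancer therapy.

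**The concern.** The window for the baseline scan is longer than the radiotherapy washout, and no rule puts the two in order. A patient can have a routine scan, have a painful lesion irradiated, consent, and start treatment with that lesion still recorded at its pre-radiation size. Later shrinkage of the lesion is measured against that size.

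ORR is the primary endpoint and there is no control arm in which the same effect would appear. A radiation effect would be credited to the combination, and the direction favors it. The same baseline feeds iORR, the waterfall plot and time to response.

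The plan accepts the principle once treatment has begun. Protocol 6.8.2 protects indicator lesions, and SAP 10.13.6 and 10.13.8 treat radiation to a tumor lesion as new anti-cancer treatment for duration of response and PFS. Radiation one week before the first dose triggers neither scoring rule, although its effect is read against the same baseline.

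**Working it through.** The plan gives no figure on this point, so the check compares the windows, looks for a rule that closes the gap, and then sizes the effect.

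**1. Exposed interval = maximum scan age − minimum washout** (Protocol 8.1.1.1, 9.3.1 and 5.2)

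- Radiotherapy, general: 28 − 14 = 14 days.
- Palliative radiotherapy: 28 − 7 = 21 days. The note covers courses of up to two weeks, so a whole 14-day course fits between the scan and the last permitted day.
- For comparison, the chemotherapy and immuno-oncology interval, "Less than 4 weeks for systemic chemotherapy and immuno-oncology therapies", gives 28 − 28 = 0 days.

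**2. Does another rule close the gap?**

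- *Last scan in the window (9.3.1).* It helps only if a further scan was taken after the radiotherapy. None is required.
- *Inclusion 5.* Judged at the first dose, a lesion irradiated after the scan lies in an irradiated area and needs demonstrated progression. Judged at the scan, it had not yet been irradiated and the rule does not apply. On either reading, progression shown before the irradiation could be taken to satisfy it.
- *Section 6.8.2.* It applies during the study. It does not clearly reach a routine scan and radiotherapy that both precede consent.
- *Confirmation.* The confirmatory scan uses the same baseline, so it does not remove the effect. SAP 11.0 also counted unconfirmed responses at the futility analysis when the confirmatory scan was pending.
- *Independent reading (8.1.1).* It is only an option, and the documents provide no new baseline for it.

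**3. How the effect enters.** If the irradiated lesion makes up a share w of the baseline sum and radiation shrinks it by a fraction s, percent change in the sum includes −100·w·s that is not due to the combination. With a single target lesion, w = 1 and all of it enters.

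**4. Size of one affected responder.** Change in ORR = 1/n.

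- n = 50: 1/50 = 2.0 points; n = 57: 1/57 = 1.8 points (planned cohorts, Protocol 9.5).
- mCRPC, if only the minimum of 35 patients with measurable disease enters: 1/35 = 2.9 points.

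Because recruitment stopped early (SAP 6.1), a cohort may be smaller than planned and the step larger.

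**5. Range under an assumption.** Let b be the true ORR, set to the benchmark in Protocol 9.4, and q the assumed share of true non-responders scored as responders. Observed ORR = b + (1 − b)q.

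| Cohort | b | q = 2% | q = 5% | q = 10% | Minimal ORR |
|---|---|---|---|---|---|
| NSCLC, ovarian | 15% | 16.7% | 19.3% | 23.5% | 23% |
| Hepatocellular | 17% | 18.7% | 21.2% | 25.3% | 25.3% |
| mCRPC | 5% | 6.9% | 9.8% | 14.5% | 10.4% |

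In a cohort of 50 with b = 15%, these q correspond to 50 × 0.85 × q = 0.9, 2.1 and 4.3 patients. The documents give no value for q, and it may be zero.

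**The case against.** **Existing rules may already cover most cases.** Inclusion 5 can fairly be read at the first dose. Several criteria equate study entry with consent, so 6.8.2 may restrict irradiation of an indicator lesion from consent onward, apart from its discretionary exception. A medical monitor confirms eligibility (4.1.1), and exclusion 20 lets the investigator exclude a patient whose therapy might confound the results. On these readings, what remains is mainly a routine scan followed by radiotherapy before consent, plus the exception. This narrows the point but does not remove it: the wording settles neither reading, and no analysis would show an affected patient.

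**Cohort limits.** The cSCC criterion concerns patients who cannot have radiotherapy. NSCLC excludes lung radiation above 30 Gy within six months. Both reduce exposure in those cohorts.

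**A false response is demanding.** The irradiated lesion must drive the whole sum, nothing else may progress, and the final analysis requires confirmation more than four weeks later. This makes the event uncommon, not impossible.

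**Recruitment has stopped.** This stands. Eligibility wording matters only if enrolment reopens.

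**Stronger readings that the documents do not support.**

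- A reader might infer that radiation shrinkage *is* being scored as response. The documents show only that it *can* be.
- A reader might extend the point to systemic drugs. Chemotherapy and immuno-oncology intervals match the scan window. The tyrosine kinase inhibitor interval falls short of it only for half-lives under 28/5 = 5.6 days. Stopping an active drug after the baseline scan would tend to work against the combination. Nothing in the documents shows how stopping an androgen receptor-targeted agent would produce a false response.
- A reader might use the chance that a cohort sits one response below its futility boundary as the size of this risk. That chance applies to any one-response error and takes no account of whether an affected patient exists. The futility analysis has also been done.

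**Conclusion.** The point holds for radiotherapy. The plan allows a target lesion to be irradiated up to 14 days after its baseline scan, or 21 days if palliative, and it neither clearly excludes that lesion from the sum nor analyses such patients separately. Any resulting bias in ORR favors the combination.

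The size is 1.8 to 2.0 points per affected responder at the planned cohort sizes of 50 to 57. How many there are is unknown. The conclusion assumes that no later pre-dose scan replaced the baseline and that inclusion 5 was not applied at the first dose. It does not show that any recorded response is false. It justifies an inexpensive check on the primary endpoint.

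**What to change.** **Now, before database lock.** Add to SAP 12.7.1 a sensitivity analysis of ORR and iORR that counts as non-responders all patients with a target lesion irradiated between the baseline scan and the first dose, and report their number by cohort. With r responders among n patients, x of them affected, the result is (r − x)/n. It is conservative, because some of those x may have responded to the combination; together with the main ORR it brackets the effect. If no patient is affected, one sentence closes the matter.

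Sources: the prior-radiation listing (SAP 12.3), the treatment dates in the cancer history (Protocol 1.3.1) and the collected scans (Protocol 8.1.1). Radiation is listed but not coded, and the documents show no link from radiation site to target lesion, so matching is by hand.

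**If enrolment reopens.** State in inclusion 5 and in 8.1.1.1 that a lesion irradiated after the baseline scan is followed as non-target, and that progression in a previously irradiated lesion must be shown on a scan taken after the irradiation. Reconcile inclusion 5, exclusion 4 and section 6.8.2 on this point.

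**Cost.** SAP wording and a review of one listing against the scans; later, protocol wording. No washout changes. A few patients may lose a target lesion.

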### Prior/concurrent clinical study experience

7. Is currently participating in or has participated in a study of an investigational agent or has used an investigational device within 4 weeks or 5 half-lives (whichever shorter) before study entry (ICF signature). Patients who have entered the follow-up phase of an investigational study may participate as long as it has been 4 weeks or 5 half-lives (whichever shorter) after the last dose of the previous investigational agent.

### Medical conditions

8. Clinically significant cardiac abnormalities including prior history of any of the following:
  - 8.1. Cardiomyopathy, with left ventricular ejection fraction  $\leq 50\%$  at screening
  - 8.2. Congestive heart failure of New York Heart Association grade  $\geq 2$
  - 8.3. History of clinically significant (i.e., active) atherosclerotic cardiovascular disease, specifically myocardial infarction, unstable angina, cerebrovascular accident within 6 months prior to the first dose of study interventions, and any clinically significant history of coronary heart disease and clinically significant artery disease within the past 5 years
  - 8.4. Prolongation of QTcF  $>450$  msec

---

- 8.5. Clinically significant cardiac arrhythmia that cannot be controlled with adequate medication
- 9. Uncontrolled hypertension defined as systolic blood pressure >160 mmHg, diastolic blood pressure >110 mmHg. Patients with uncontrolled hypertension should be medically managed on a stable regimen to control hypertension prior to study entry (ICF signature).
- 10. Has undergone prior allogeneic hematopoietic stem cell transplantation within the last 5 years. Patients who have had a transplant more than 5 years ago are eligible as long as there are no symptoms of graft versus host disease.
- 11. Has had an allogeneic tissue/solid organ transplant
- 12. Has a diagnosis of immunodeficiency or is receiving chronic systemic steroid therapy (in dosing exceeding 10 mg daily of prednisone equivalent) or any other form of immunosuppressive therapy within 7 days prior to the first dose of study interventions
- 13. History of or serology positive for HIV. A locally performed HIV test is required during screening.
- 14. Has a known additional malignancy that is progressing or has required active treatment within the past 5 years. Patients with basal cell carcinoma of the skin or carcinoma *in situ* excluding carcinoma *in situ* of bladder that have undergone potentially curative therapy are not excluded.
- 15. Has known active central nervous system metastases and/or carcinomatous meningitis. Patients with previously treated brain metastases may participate provided they are radiologically stable, i.e., without evidence of progression for at least 4 weeks by repeat imaging (note that the repeat imaging should be performed during study screening), clinically stable and without requirement of steroid treatment for at least 14 days prior to the first dose of study interventions.
- 16. Has severe hypersensitivity (grade  $\geq 3$ ) to pembrolizumab and/or any of its excipients
- 17. Has an active autoimmune disease that has required systemic treatment in the past 2 years (i.e., with use of disease-modifying agents, corticosteroids, or immunosuppressive drugs). Replacement therapy (e.g., thyroxine, insulin, or physiologic corticosteroid replacement therapy for adrenal or pituitary insufficiency) is not considered a form of systemic treatment and is allowed.
- 18. Has a history of (non-infectious) pneumonitis/interstitial lung disease that required steroids or has current pneumonitis/interstitial lung disease
- 19. Has an active infection requiring systemic therapy
- 20. Has a history or current evidence of any condition, therapy, or laboratory abnormality, or other circumstance that might confound the results of the study or interfere with the patient's participation for the full duration of the study, such that it is not in the best interest of the patient to participate, in the opinion of the treating investigator
- 21. Has a known psychiatric or substance abuse disorder that would interfere with the patient's ability to cooperate with the requirements of the study

## 5.3 Lifestyle considerations

### 5.3.1 Meals and dietary restrictions

Patients should maintain a normal diet unless modifications are required to manage an AE such as diarrhea, nausea, or vomiting.

### 5.3.2 Contraception

Nanrilkefusp alfa and pembrolizumab may have adverse effects on a fetus *in utero*. Furthermore, it is not known if nanrilkefusp alfa and pembrolizumab have transient adverse effects on the composition of sperm.

Patients should be informed that taking the study medication may involve unknown risks to the fetus (unborn baby) if pregnancy were to occur during the study. If there is any question that a patient of childbearing potential will not reliably comply with the requirements for contraception, that patient should not be entered into the study.

Please also see section [5.1](#).

